## **12.3 Analysis of Endpoints**

### ***12.3.1 Analysis of Primary Endpoints***

Median rPFS will be estimated using Kaplan-Meier methodology. Greenwood's formula will be used to calculate 95% CIs for the Kaplan-Meier estimates.

### ***12.3.2 Analysis of Secondary Endpoints***

The median OS will be estimated using Kaplan-Meier methodology. Greenwood's formula will be used to calculate 95% CIs for the Kaplan-Meier estimates. The proportion of men with a meaningful decrease in PSA from baseline (30% and 50% declines will both be used) will be summarized with a binomial point estimate and corresponding 95% binomial CI. Likewise, the proportion of patients with a tumor response (modified RECIST response of CR or PR) will also be estimated with a binomial point estimate and 95% CI.

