### 4.2 Inclusion Criteria

1. Age >18 years.
2. Documented histological or cytological diagnosis of prostate carcinoma.
3. Evidence of metastatic PC on imaging (bone scan and/or CT/MRI scan)
  - a. Patients with liver metastases must have biopsy proven evidence of metastatic prostate cancer in the liver
4. Agree to undergo a biopsy of at least one metastatic site or primary prostate prior to beginning therapy. Adequate archival metastatic tissue can be used if available in lieu of a biopsy if done when patient had CRPC and within 6 months the start of treatment.
5. Agree to undergo a biopsy of at least one metastatic site or primary prostate after 3 weeks of therapy (biopsy must be between day 21 and day 24 of treatment). Re-biopsy of same pre-treatment biopsy soft tissue site especially liver metastases is preferred.
6. Serum testosterone level less than 50 ng/dL. Subjects without prior orchiectomy must be currently taking and willing to continue luteinizing hormone-releasing hormone (LHRH) analogue (agonist or antagonist) therapy until permanent discontinuation of study treatment.
7. Documented progressive metastatic CRPC based on at least one of the following criteria:
  - a. PSA progression according to Prostate Cancer Working Group 3 (PCWG3) criteria
  - b. Objective radiographic progression, according to PCWG3 criteria
8. ECOG performance status of 0-1
9. Recovery to baseline or  $\leq$  Grade 1 CTCAE v4 from toxicities related to any prior treatments, unless specified below or AE(s) are clinically nonsignificant and/or stable on supportive therapy.
10. Adequate organ and marrow function, based upon meeting all of the following laboratory criteria **within 14 days before first dose of study treatment**:
  - a. Absolute neutrophil count (ANC)  $\geq 1500/\text{mm}^3$  ( $\geq 1.5 \text{ GI/L}$ ) without granulocyte colony-stimulating factor support
  - b. White blood cell count  $\geq 2500/\text{mm}^3$  ( $\geq 2.5 \text{ GI/L}$ )
  - c. Platelets  $\geq 100,000/\text{mm}^3$  ( $\geq 100 \text{ GI/L}$ ) without transfusion.
  - d. Hemoglobin  $\geq 9 \text{ g/dL}$  ( $\geq 90 \text{ g/L}$ )
  - e. Total bilirubin  $\leq 1.5 \times \text{ULN}$  (for subjects with Gilbert's disease  $\leq 3 \times \text{ULN}$ )
  - f. Serum albumin  $\geq 2.8 \text{ g/dL}$
  - g. Serum creatinine  $\leq 2.0 \times \text{ULN}$  or calculated creatinine clearance  $\geq 30 \text{ mL/min}$  ( $\geq 0.5 \text{ mL/sec}$ ) using the Cockcroft-Gault equation:

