#### 4.4 Molecular Eligibility

To be eligible, a patient's tumor must have evidence of gene amplification, an activating mutation, or overexpression of one of the following genes: MET, KIT, RET, VEGFR-1, VEGFR-2, VEGFR-3, FLT3, AXL, TRKB, or TIE2. In the event of activating mutations, the observed mutation must be of Level 1, Level 2, or Level 3 as annotated by OncoKB ([www.oncokb.org](http://www.oncokb.org)). Eligibility can be met by **at least one** of the following diagnostic tests:

- 1) DNA sequencing of a metastatic tumor biopsy specimen showing gene amplification or activating mutation using a CLIA-certified assay. Tumor tissue samples must have been collected within 6 months of enrollment.
- 2) Protein overexpression in a metastatic tumor biopsy specimen determined by immunohistochemistry (IHC) showing 3+ protein expression using a CLIA-certified assay. These

- include common in-house KIT and commercial reference labs for panTRK (*e.g.* NeoGenomics) and cMET (*e.g.* NeoGenomics, Caris, Mayo Clinic).
- 3) CLIA-certified commercial cell free DNA assay (either Guardant360 or FoundationOneLiquid assay) reporting gene amplification or activating mutation *within 6 months of enrollment*.
    - a. For the Guardant360 Liquid Biopsy amplification must be at least (++) or (+++) for to meet eligibility.
    - b. For the FoundationOneLiquid assay, amplification will be eligible. Reports that have an “equivocal” or “subclonal” designation will not be eligible.
  - 4) Any non-CLIA certified assay such as RNA expression profiling of a metastatic tumor biopsy specimen showing overexpression must be confirmed by a CLIA-certified assay (*i.e.*, immunohistochemistry showing 3+ protein expression)

Patients who do not meet molecular eligibility criteria will be allowed to enroll if they have liver metastases that meet RECIST criteria for measurable disease. Patients with prostate adenocarcinoma or NEPC will be allowed to enroll.

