### **10.2 Measurable soft-tissue lesions**

When evaluating soft-tissue lesions, the following PCWG-modified RECIST response criteria for target(soft-tissue) lesions definitions apply.

- Complete response (CR): the disappearance of clinical and radiological evidence of all target lesions and normalization of tumor marker levels
- Partial response (PR): a decrease from baseline  $\geq 30\%$  in the sum of the LD of all target lesions
- Progressive disease (PD): an increase  $\geq 20\%$  in the sum of the LD of all target lesions based on the smallest sum LD since treatment started or the appearance of one or more new lesions or the appearance of new lesions
- Stable disease (SD) : neither sufficient shrinkage to qualify for PR nor sufficient increase to qualify for PD based on the smallest sum LD recorded since treatment started

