## **12.2 Sample Size/Accrual Rate**

Sample size for the entire trial will be 30 patients. Accrual will not mandate an equal number of each of the qualifying molecular abnormalities. The sponsor retains the right to terminate enrollment in any specific genetic alteration if no significant benefit is observed in that given cohort.

Any enrolled subject who withdraws for any reason prior to a full 28 days of treatment and assuming he did undergo the second biopsy ("on treatment biopsy") will be replaced and not incorporated into the analysis.

Accrual is anticipated to be 1-4 patients per month in total across all study sites

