## **12.4 Analysis of Exploratory Endpoints**

Data generated will include IHC scores for targets of cabozantinib, scores for immune cell infiltrate, whole exome sequencing (WES), targeted DNA sequencing, and RNA-Seq for expression. Measures with significant changes from baseline will be determined using the appropriate two-sample test: either a paired t-test or Wilcoxon signed rank test for continuous measures and a chi-square test for categorical variables. The Benjamini-Hochberg procedure will be used to control the false discovery rate for the genomic measurements (DNA, RNA Seq). If the variables are ordinal, an analysis will be done for the proportion of changes that were "positive", "negative", or "no change". An assessment of differences between groups (*e.g.* patients with and without tumor response) will be evaluated with a two-sample t-test or Wilcoxon rank sum test, whichever is most appropriate, for continuous measurement. A chi-square or Fisher's exact test will be used to compare categorical variables between groups of interest. A comparison of time-to-event variable between subgroups of interest will be done with a log-rank test. Associations of variables with time-to-event outcomes will be made with Cox proportional hazard models. For baseline variables the survival clock will start at baseline; for

variables measured later, a landmark analysis will be done starting the survival clock at the time the data were obtained (and removing patients who had the event of interest before that time). We will also perform a Cox regression that treats multiple measurements of a variable as time-dependent

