### ***12.5.2 Evaluation of Response***

All subjects included in the study will be assessed for response to treatment if they have received at least 3 cycles of therapy.

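### The tumor response proportion has no measurable-disease condition, so men with bone-only disease, all of them alteration-positive, would naturally be counted as non-responders

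*Combined protocol and SAP*

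**What the plan says.** **Analysis.** Section 12.3.2 treats response as a binomial proportion with a 95% CI: "the proportion of patients with a tumor response (modified RECIST response of CR or PR) will also be estimated". It gives no denominator beyond patients. Section 12.5.2 comes closest to an evaluable set: "All subjects included in the study will be assessed for response to treatment if they have received at least 3 cycles of therapy". Under section 12.2, a subject who withdraws before a full 28 days of treatment but has had the on-treatment biopsy "will be replaced and not incorporated into the analysis". None of these sections mentions measurable disease. Section 12.4 names, as an example of a group comparison, "patients with and without tumor response".

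**Scoring.** Section 10.2 states that "the following PCWG-modified RECIST response criteria for target(soft-tissue) lesions definitions apply", and CR and PR are both worded in terms of target lesions. Section 10.1 says that bone scans also feed best overall response, through criteria specific to the protocol. The bone criteria in section 10.4 only record whether new lesions have appeared and ask for confirmation if lesions vanish. They assign neither CR nor PR.

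**Entry.** Criterion 3 of section 4.2 asks for "Evidence of metastatic PC on imaging (bone scan and/or CT/MRI scan", so a positive bone scan is enough. Criterion 11 requires a qualifying alteration of men without liver metastases and asks nothing about measurable disease. Section 4.4 admits men who fail the molecular criteria only "if they have liver metastases that meet RECIST criteria for measurable disease".

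**The concern.** A correctly enrolled man with bone-only disease has no target lesion. He cannot reach CR or PR, even if his bone scan clears, yet nothing removes him from the response denominator. The proportion would then mix two things: how often measurable tumors shrink, and how many men had measurable tumors to begin with.

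The marker analyses are more exposed. Sections 4.2 and 4.4 together mean that every man without a target lesion carries an alteration. Men who could not be scored would therefore enter the group without response from one marker group only, and that is the group in which section 2.3 predicts benefit. Bone findings are not a side issue for this drug: section 2.2.1 reports a 42% bone scan response at week 12 in COMET-1, which enrolled bone-dominant disease.

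Sections 1 and 1.2.1 name the radiographic response proportion as the primary objective, so its denominator should not be left to interpretation.

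**Working it through.** **The plan's own figure.** Section 12 gives no precision for the response proportion. Its only such figure is the 95% CI of 31.1-68.9% for rPFS in section 12.1. It reproduces as 0.5 ± 1.96 × √(0.25/27) = 0.5 ± 0.189 (n = 28 gives 31.5-68.5%). It has no bearing on this point.

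**Inputs.** Total sample 30 (section 12.2). Liver-metastasis patients up to 28 (section 12.1), which is a ceiling. The plan gives neither the number of men without a target lesion, b, nor the true response rate in measurable disease, p. I assume b = 2, 5 or 10 and p = 20% or 30%. b = 2 is the case in which all 28 liver places are filled by men with measurable disease.

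**Step 1: overall proportion.** If all 30 reach three cycles and men without a target lesion count as non-responders, the reported proportion is p × (30 − b)/30.

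| b | factor | 20% becomes | 30% becomes |
|---|---|---|---|
| 2 | 28/30 = 0.93 | 18.7% | 28.0% |
| 5 | 25/30 = 0.83 | 16.7% | 25.0% |
| 10 | 20/30 = 0.67 | 13.3% | 20.0% |

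**Step 2: marker comparison.** Assume the true rate is 30% with and without an alteration, and that the 30 − b measurable men split about equally between the two. All b men fall in the alteration-positive group. The observed rate there is 0.30 × (measurable alteration-positive)/(measurable alteration-positive + b), against 30% in the other group.

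| b | calculation | observed rate | odds ratio (truth = 1) |
|---|---|---|---|
| 2 | 0.30 × 14/16 | 26% | 0.83 |
| 5 | 0.30 × 12/17 | 21% | 0.63 |
| 10 | 0.30 × 10/20 | 15% | 0.41 |

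For b = 5, the odds ratio is (0.212/0.788)/(0.30/0.70) = 0.63. If only about a quarter of the measurable men are alteration-positive (7, 6 and 5 men), the odds ratios are 0.71, 0.46 and 0.26.

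**Step 3: the three-cycle rule.** Three 28-day cycles are 84 days, or 12 weeks, which is when the first on-treatment scan is due. Men who stop before then leave the denominator.

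- With b = 5 and 8 responders among 25 measurable men, the measurable-disease rate is 8/25 = 32.0%. If 6 non-responders stop early, the plan's figure is 8/(30 − 6) = 33.3%, which is higher.
- With b = 10 and 6 responders among 20, the measurable-disease rate is 30.0%. The same 6 losses give 6/24 = 25.0%, which is lower.

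The two distortions pull in opposite directions, and either can dominate.

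**The case against.** The strongest reply is that the plan never calls bone-only men non-responders. Section 12.3.2 refers to a modified RECIST response, and the criteria stand under a heading about measurable soft-tissue lesions, so such men could be treated as not evaluable. It is fair that non-responder status is an inference. But section 12.5.2 sends every subject with three cycles to response assessment, and no not-evaluable category is provided, so counting them is the more natural reading. On the other reading the denominator is still unset and could be chosen after the results are known.

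Section 10.1 does bring bone scans into best overall response. That shows intent, but section 10.4 supplies no category through which a bone finding could become a response.

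The effect may also be small. With 28 of 30 men measurable, 20% becomes 18.7%, a shift of 1.3 points beside an exact 95% CI of 7.7-38.6% for 6/30. For the overall rate this stands if the liver places fill. However, 28 is only a ceiling, and section 3.1 still describes the 30 as molecularly selected and contemplates 12 subjects with one alteration (some of whom may also have liver metastases).

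Finally, section 12 makes rPFS primary and tumor response secondary, and bone-only men contribute fully to rPFS because section 10.6 counts progression in bone. That is correct. The mismatch with the stated primary objective is a separate matter and does not make this one more serious.

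Two stronger readings are tempting. One is that the proportion is taken over every enrolled man; sections 12.5.2 and 12.2 rule that out. The other is that the reported overall rate must be too low; the three-cycle rule means the documents do not establish that.

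**Conclusion.** The point holds as a defect in the response denominator. Applied as written, sections 12.3.2, 12.4 and 12.5.2 most naturally place men who cannot respond by definition among the non-responders, and all of those men are alteration-positive.

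Taken alone, this multiplies the overall proportion by the measurable fraction: a relative loss of about 7% with 2 of 30 such men, and factors of 0.83 and 0.67 with 5 and 10. The counts of 5 and 10, the response rates and the marker split are assumptions; the plan gives none of them. The net direction of the overall rate is not fixed. The distortion of comparisons involving the target alterations is one-sided, because entry puts every man without a target lesion on the same side.

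**What to change.** - In sections 12.3.2 and 12.5.2, define the response proportion among treated patients with at least one measurable soft-tissue target lesion at baseline. This fixes the denominator before treatment and does not depend on reaching three cycles.
- State that men without a target lesion are not evaluable for RECIST response, and give the proportion over all patients as a supportive figure.
- In section 12.4, use the same measurable-disease set for every responder versus non-responder comparison.
- Keep men without target lesions in the rPFS, OS and PSA analyses. Describe their bone findings under section 10.4, since section 12 defines no bone-scan response endpoint.

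The cost is wording: baseline CT/MRI is already in the Schedule of Assessments. The denominator shrinks and the interval widens somewhat. With 5 bone-only men and 8 responders, 8/25 = 32.0% has an exact 95% CI of 14.9-53.5% (38.6 points wide), against 12.3-45.9% (33.6 points) for 8/30 = 26.7%.

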## **12.4 Analysis of Exploratory Endpoints**

Data generated will include IHC scores for targets of cabozantinib, scores for immune cell infiltrate, whole exome sequencing (WES), targeted DNA sequencing, and RNA-Seq for expression. Measures with significant changes from baseline will be determined using the appropriate two-sample test: either a paired t-test or Wilcoxon signed rank test for continuous measures and a chi-square test for categorical variables. The Benjamini-Hochberg procedure will be used to control the false discovery rate for the genomic measurements (DNA, RNA Seq). If the variables are ordinal, an analysis will be done for the proportion of changes that were "positive", "negative", or "no change". An assessment of differences between groups (*e.g.* patients with and without tumor response) will be evaluated with a two-sample t-test or Wilcoxon rank sum test, whichever is most appropriate, for continuous measurement. A chi-square or Fisher's exact test will be used to compare categorical variables between groups of interest. A comparison of time-to-event variable between subgroups of interest will be done with a log-rank test. Associations of variables with time-to-event outcomes will be made with Cox proportional hazard models. For baseline variables the survival clock will start at baseline; for

variables measured later, a landmark analysis will be done starting the survival clock at the time the data were obtained (and removing patients who had the event of interest before that time). We will also perform a Cox regression that treats multiple measurements of a variable as time-dependent

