### *Immune Biomarkers*

Preclinical studies in a PTEN/p53-deficient murine PC model showed that cabozantinib rapidly eradicated poorly differentiated tumors [29]. This anti-tumor effect was associated with enhanced release of neutrophil chemotactic factors from tumor cells, predominantly CXCL12 - resulting in robust infiltration of neutrophils into the tumor. This study suggested that cabozantinib triggered a neutrophil-mediated anticancer innate immune response.

Cabozantinib also increased Treg infiltration, immune regulation, and T-cell mediated killing by upregulating MHC-I molecules and markers (*e.g.* ICAM-1, Fas) in a VEGFR2- and MET-expressing cell line [30]. Furthermore, cabozantinib alone or in combination with immune checkpoint blockade decreases myeloid-derived suppressor cells (MDSCs), which are associated with a tumor permissive

microenvironment, which increases immune surveillance [31, 32].

In order to test the systemic effects of cabozantinib treatment in PC patients on immune signals and cytokines related to possible immunity-dependent effects of cabozantinib, we will assess gene expression and immune cell infiltrates at baseline and after initiation of cabozantinib treatment. We will also measure circulating levels of cytokines. The primary hypothesis will be that treatment will reduce systemic levels of cytokines associated with a suppressive myeloid microenvironment. To that end, we will quantify pre and on treatment levels of the following cytokines: interleukin-8, interleukin-6 and interleukin-1 all of which have been associated with a non-permissive tumor microenvironment. As a secondary hypothesis, we will test whether levels of pro-inflammatory cytokines are increased in a compensatory manner – those studies will focus on the TH1 cytokines particularly interferon gamma, interleukin-12 and interleukin-2. Of note, prior studies by our group suggested that a TH1 cytokine signature was associated with a decreased risk of prostate cancer progression in a population-based study.

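### Section 12.4 names a chi-square test for within-patient change in binary or nominal biomarkers; that test does not use the pairing, and a paired test should be named

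*Combined protocol and SAP*

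**What the plan says.** Section 12.4 (Analysis of Exploratory Endpoints) sets the rule for change over time: "Measures with significant changes from baseline will be determined using the appropriate two-sample test". It then lists "either a paired t-test or Wilcoxon signed rank test for continuous measures and a chi-square test for categorical variables".

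The data are paired by design. Section 2.5 (Immune Biomarkers) states "we will assess gene expression and immune cell infiltrates at baseline and after initiation of cabozantinib treatment". Section 4.2 requires a pre-treatment biopsy or adequate archival tissue, and a second one: "Agree to undergo a biopsy of at least one metastatic site or primary prostate after 3 weeks of therapy". On location it adds "Re-biopsy of same pre-treatment biopsy soft tissue site especially liver metastases is preferred".

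Two other sentences in Section 12.4 limit the point. Ordinal variables have their own rule: "If the variables are ordinal, an analysis will be done for the proportion of changes" that were positive, negative or absent. Comparisons between patient groups are also covered separately: "A chi-square or Fisher's exact test will be used to compare categorical variables between groups of interest".

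The number of pairs is capped by Section 12.2: "Sample size for the entire trial will be 30 patients". No McNemar, Bowker or Stuart-Maxwell test is named anywhere. No significance level, marker rate or within-patient correlation is given for these analyses.

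**The concern.** The sentence asks whether a marker changed within patients. For continuous measures it names tests that use the pairing. For categorical measures it names one that, as written, does not. The separate sentence on groups of interest shows that this chi-square test is not meant for comparing different patients.

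There are two literal ways to run it. On a table of time point by category, it treats a patient's two samples as if they came from two people. On the cross-table of baseline by on-treatment category, it asks whether the two results are associated, so a marker that never changes gives a strongly significant result.

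At stake is how well the trial uses its paired samples. The on-treatment biopsy is invasive, at most 30 pairs will exist, and genomic measures also pass through Benjamini-Hochberg control, which makes an unnecessarily large p-value more costly.

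**Working it through.** The plan gives no figure to reproduce, so the check compares the tests directly.

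**Inputs.** From the documents: at most 30 pairs (Section 12.2). Assumed: two-sided 0.05; binary marker; positivity before and after, p1 and p2; within-patient correlation ρ from 0 to 0.7; 20 pairs as a sensitivity value for missing or inadequate biopsies.

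**Why pairing matters.** With no true change and positivity p, the difference in proportions has variance 2p(1−p)(1−ρ)/n. The unpaired chi-square uses 2p(1−p)/n. Its true type I error is therefore about 2Φ(−1.96/√(1−ρ)):
- ρ = 0.3: 1.96/0.837 = 2.34, giving 1.9%.
- ρ = 0.5: 1.96/0.707 = 2.77, giving 0.6%.

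**Exact enumeration.** For each setting, p11 = p1·p2 + ρ√[p1(1−p1)p2(1−p2)], p10 = p1 − p11, p01 = p2 − p11, and p00 is the remainder. Every possible paired 2×2 table was weighted by its multinomial probability, and the rejections were added up. The chi-square is Pearson's without continuity correction.

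No change, 40% positive, n = 30: the chi-square rejects 1.9%, 0.6% and 0.06% of the time at ρ = 0.3, 0.5 and 0.7. At ρ = 0 it holds its level (4.9% to 5.2% at 30% and 50% positive). For comparison, at 30% and 50% positive, mid-p McNemar rejects 4.0% to 4.2% at ρ = 0.3 and 3.3% to 3.7% at ρ = 0.5; exact McNemar rejects 2.1% to 2.3% and 1.4% to 1.8%.

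Power, 30% to 55%, n = 30. At ρ = 0.5, for example, p11 = 0.165 + 0.5 × 0.228 = 0.279, p10 = 0.021 and p01 = 0.271.

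| ρ | Chi-square, unpaired | Exact McNemar | Mid-p McNemar |
|---|---|---|---|
| 0 | 51% | 40% | 48% |
| 0.2 | 51% | 47% | 56% |
| 0.3 | 51% | 52% | 62% |
| 0.5 | 50% | 68% | 79% |

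Sensitivity, 20 pairs, 30% to 50%:

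| ρ | Chi-square, unpaired | Exact McNemar | Mid-p McNemar |
|---|---|---|---|
| 0 | 24.5% | 15.1% | 21.7% |
| 0.3 | 20.4% | 18.3% | 27.8% |
| 0.5 | 16.6% | 20.0% | 33.2% |

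**Example, time-by-category table.** 9 of 30 positive at baseline and 15 of 30 on treatment; six patients switch to positive and none switch back.
- Unpaired chi-square: (15−9)² × 60/(24 × 36) = 2.5, p = 0.114.
- McNemar: (6−0)²/6 = 6.0, p = 0.014.
- Exact McNemar: 2 × 0.5⁶ = 0.031. Mid-p: 0.031 − 0.5⁶ = 0.016.

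**Example, cross-table.** 12 of 30 positive both times: 10 stay positive, 16 stay negative, two switch each way. There is no net change, and McNemar's statistic is (2−2)²/4 = 0. The chi-square for association is 30 × (10 × 16 − 2 × 2)²/(12 × 18 × 12 × 18) = 15.6, far above 3.84.

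**The case against.** The best defence is that the wording is loose rather than wrong. The sentence asks for the appropriate test, and the label two-sample also introduces the paired t-test, so it cannot be taken literally. McNemar's test is itself a chi-square test on the patients who switch, and a statistician might well run it. That is possible, but the text does not say so, and someone following it as written would not be led there.

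A reader might infer that the trial will lose much of its power to detect biomarker change. The documents do not support that as a general statement. They give no correlation, and same-site re-biopsy is only preferred. At zero correlation the unpaired test loses nothing. The large gap at 0.5 assumes nearly one-directional change: about 27% of patients switch one way and 2% the other, and the highest correlation those rates allow is (0.30 − 0.165)/0.228 = 0.59.

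A reader might also infer that any paired test would be better. Exact McNemar is not: with 30 pairs it gains about one point at correlation 0.3 and is worse below that, and with 20 pairs it is still slightly worse at 0.3. This part of the objection stands and decides which remedy to name.

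A third inference, that the exploratory objectives as a whole depend on this test, also goes too far. Expression and cytokine levels are continuous and have paired tests. Ordinal staining or infiltrate scores fall under the direction-of-change rule, which keeps the pairing. No primary or secondary analysis, sample size or decision rule is touched, and the paired data remain available for reanalysis.

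**Conclusion.** The point holds within limits. For binary or nominal exploratory markers, such as an alteration being present or absent, Section 12.4 names a test that either ignores the pairing or answers a different question.

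If it is run on before and after counts with positive correlation, the error is conservative: changes are missed, and false positives are not inflated. With mid-p McNemar as the comparator, 30 pairs and a 30% to 55% shift, the power given up is about 11 points at correlation 0.3 and 29 at 0.5, and none at zero. These sizes rest on assumed rates, correlation and significance level. Some positive correlation is plausible because both samples come from one patient, but its value is unknown. That the literal test is unsuited to within-patient change does not depend on those assumptions.

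**What to change.** In Section 12.4:
- Describe the change-from-baseline tests as paired instead of two-sample.
- For binary markers, replace chi-square with the mid-p McNemar test. Prefer it to exact McNemar, which is itself conservative at this size.
- For more than two nominal categories, name one test in advance: Stuart-Maxwell (equal category proportions at both times) or Bowker (symmetry of switches).
- Keep chi-square or Fisher's exact test only for comparisons between groups of patients.

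The cost is one or two sentences. Sampling, data collection, sample size and the other analyses do not change.
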